The primary objective will be evaluated using Simon's two-stage design. The null hypothesis that the true ORR is (5%, 7% and 10% for colorectal cancer, ovarian cancer and cervical cancer, respectively) will be tested against a one-sided alternative. The design yields a type I error rate of 5% and power of 80% for each of the three indications individually. No correction for multiplicity will be done. In addition to tabulate the result of the statistical tests, results will be summarized descriptively.

Various solid tumors cohort: Safety

The safety and tolerability of pembrolizumab and birinapant will be based on results of reported SAEs, AEs, vital sign measurements, physical examinations, clinical laboratory information, ECOG performance status, and concomitant medications. Safety data will be summarized descriptively. Exposure to study drug and reasons for discontinuation will be tabulated.

Adverse events will be coded using the current *Medical Dictionary for Regulated Activities* (MedDRA) classification system, and will be summarized by system organ class and preferred term.

Additional safety analyses may be determined in order to most clearly describe toxicity rates and to further define the

safety profile of pembrolizumab and birinapant.

Secondary Endpoints:

Cohorts in colorectal cancer, ovarian cancer and cervical cancer: Safety

The safety and tolerability of pembrolizumab and birinapant will be based on results of reported SAEs, AEs, vital sign measurements, physical examinations, clinical laboratory information, ECOG performance status, and concomitant medications. Safety data will be summarized descriptively by cohort and also summarized descriptively over cohorts within each of the two phases of the protocol. Exposure to study drug and reasons for discontinuation will be tabulated.

Adverse events will be coded using the current *Medical Dictionary for Regulated Activities* (MedDRA) classification system, and will be summarized by system organ class and preferred term.

Additional safety analyses may be determined in order to most clearly describe toxicity rates and to further define the safety profile of pembrolizumab and birinapant.

All Cohorts: Clinical Activity

Efficacy, as defined by PFS, CBR, Time to response and Duration of response, will be assessed through RECIST v 1.1 and until response or progression. Overall survival will also be assessed.

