3.3.1.2 Dose expansion phase

The dose expansion phase will comprise 4 cohorts of 26-30 patients, as follows:

1. Colorectal cancer (28 patients will be recruited)
2. Ovarian cancer (27 patients will be recruited)
3. Cervical cancer (26 patients will be recruited)
4. Various solid tumors (30 patients will be recruited, including 5 patients with each of the 6 following tumor types: (Small cell lung cancer; Cholangiocarcinoma; Gastroesophageal carcinoma; Mesothelioma; Head and Neck Squamous Cell Carcinoma (HNSCC)-checkpoint inhibitor-naïve; and HNSCC checkpoint inhibitor-experienced)

A Simon's 2-stage design (Simon 1989) will be used for each of the cohorts in colorectal cancer, ovarian cancer and cervical cancer, as outlined in Table 4. A predefined interim analysis allowing stopping each of these cohorts for futility and safety will be conducted in the first stage to limit undue exposure before further inclusion into a given cohort.

The interim analyses will be based on at least 6 and most 13 patients having completed from 9 up to 27 weeks of treatment (3 to 9 cycles) in the colorectal cancer cohort and based on at least 6 and at most 16 and 15 patients in the ovarian cancer cohort and cervical cancer cohort, respectively.

The Simon's two-stage design as outlined in Table 4 yields a type I error rate of 0.05 and statistical power of 0.80 for each of the three main cohorts described above using a one-sided test when the true response rate is 20% for colorectal cancer, 25% for ovarian cancer and 30% for cervical cancer. No formal sample size or power calculation will be performed for the fourth cohort.

Note that one additional patient will be included in each cohort compared to what is stated in Table 4. This patient will only be included in the interim analysis in case a patient drops out in that cohort. Thus, the number of included patients in each cohort will be 27+ 1 (CRC), 26+1 (ovarian) and 25+1 (cervical). In all cases this extra patient will be included in the main/end analysis. If the predefined level for success in a given cohort is reached prior to the stipulated number of patients being enrolled/completed, enrollment in that cohort may be discontinued.

4. Assessments

An overview of the time points of measurements for each assessment is given in Table 5 (Schedule of Study Procedures and Assessments) in Appendix 1.

4.1 *Disposition and Other Supporting Assessments*

4.1.1 *Patient Compliance*

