5.3 General Principles for Presenting Study Data

All statistical analyses will be performed at SDS using SAS® (Version 9.3 or higher, SAS Institute Inc., Cary, NC, USA). All statistical analyses will be performed after this SAP is finalised and approved and the study database is locked.

Continuous data will be summarized using descriptive statistics where the following parameters will be reported:

- Number of observations (n),
- Mean,
- Median,
- Standard deviation (SD),

- Range (Min, Max)

Categorical data will be presented as the number and percentage of patients.

Time to event endpoints defined in Section 4.2.3 (e.g. duration of response, OS and time to iCPD) will be analysed using Kaplan-Meier methods taking censoring into account. The Kaplan-Meier plot and corresponding estimate of the median value with 95% confidence interval will be reported.

All tests will be one-sided and performed at the 5% significance level. When reporting the results of significance tests, p-values will be reported together with 2-sided 90% confidence intervals.

Throughout the report, the number of decimal places given for the summary statistics; mean, STD, confidence interval and median values will exceed that of the source data by one. Minimum and maximum will have the same number of decimal places as the source data. For relative frequencies, integer with one decimal and %-sign will be presented and for p-values four (three) decimals will be reported.

Percentages will be based on number of patients with data at a certain time point with the exception of presentations of medical history, medications and AEs where the percentages will be based on the number of patients in the study population.

In general, all data will be listed, sorted by phase of study, cohort and patient, and when appropriate by cycle within patient. All summary tables will be structured with a column for cohort and will be annotated with the total population size relevant to that table/cohort, including any missing observations. Summary tables will include summaries for visits for Cycle 1 (Screening, Day 1 pre dose, Day 1 post dose, Day 8 pre dose, Day 8 post dose and Day 22 End of Cycle 1 as appropriate) whereas subsequent cycles will be summarized with summary statistics for the minimum and maximum observed value during the subsequent cycles.

The two phases of the study will be summarized separately. In addition, cohorts from phase 1 and phase 2 may be combined and summarized if appropriate.

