5.6.1 Primary Efficacy Analysis

The primary endpoint will be summarized for the Efficacy Evaluable Population in accordance with Section 5.3.

The primary efficacy analysis for each of the three main cohorts in the dose expansion phase of the protocol will be evaluated using Simon’s two-stage design (Simon 1989). The null hypothesis that the true response rate (π) is π_0 will be tested against the one-sided alternative $H_A: \pi > \pi_0$ in each of the three cohorts with π_0 , π_1 , n_1 , n , r_1 and r_2 as in Table 4 as follows. In the first stage, n_1 patients will be accrued. If there are r_1 or fewer responses in these n_1 patients, the cohort will be stopped and the p-value for the test will be reported as not significant (no p-value will be calculated). Otherwise, $n - n_1$ additional patients will be accrued for a total of n patients. The null hypothesis will be rejected if r_2+1 or more responses are observed in n patients.

Table 4 Simon’s two-stage design settings in each of the three main cohorts

Indication	Response rate (ORR)		n_1 (# patient in the 1 st stage)	n (Total #patients)	r_1 (Continue with stage 2 if $>r_1$ responses in stage 1)	r_2 (p-value ≤ 0.05 if $>r_2$ responses after stage 2)
	Poor drug (π_0)	Good drug (π_1)				
Colorectal cancer	$\leq 5\%$	$\geq 20\%$	13	27	0	3

Ovarian cancer	$\leq 7\%$	$\geq 25\%$	16	26	1	4
Cervical cancer	$\leq 10\%$	$\geq 30\%$	15	25	1	5

In case the total number of evaluable patients do not equal the planned number of patients (n in Table 4), the statistical inference of the ORR will take account of the actual total number of evaluable patients, n^* , as suggested in Koyama and Chen (2007). With a modified stage 2 sample size, the p-value will be calculated as follows.

- i. Find π^* such that $P_{\pi}(X_2 > r_2 - x_1 | n_2) = P_{\pi_0}(X_2 \geq x_2 | n_2^*)$
- ii. Compute the p-value by

$$\sum_{x=r_1+1}^{n_1} P_{\pi_0}(X_1 = x | n_1) A(x, n_2, \pi^*)$$

Here $n_2 (= n - n_1)$ denotes the planned number of patients in the second stage, n_2^* the actual number of patients in the second stage and X_2 denotes the number of responses among those n_2 patients. The p-value will be calculated as above even if $n_2^* = n_2$. In that case it simplifies to the original Simon's 2-stage design with rejection regions as in Table 4.

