The point estimate of response rate and the corresponding 90% confidence interval will be obtained by inverting the hypothesis testing. Compute the p-value for testing $H_0: \pi \leq \pi'_0$ versus $H_A: \pi > \pi'_0$ as above. The 90% confidence interval for π is the collection of π'_0 such that the corresponding p-value is within [0.05, 0.95]. The value of π'_0 which gives a p-value of 0.5 will be the point estimate of the response rate (π).

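### When stage 2 has no responses, the SAP 5.6.1 formula ignores the stage-1 count, so the ORR estimate, interval and p-value can fall below those of a cohort with fewer responders

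*SAP*

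**What the plan says.** SAP 5.6.1 tests each of the three main cohorts with a Simon two-stage design (Table 4). To allow for a second stage of actual size n2* instead of the planned n2, it calculates the p-value in two steps. Step i finds a rate π* at which the planned-size conditional rejection probability, given the observed stage-1 count x1, equals the probability under the tested rate of x2 or more responses among n2* patients. Step ii sums, over stage-1 counts above r1, the stage-1 probability under the tested rate times A(x, n2, π*). A is not defined.

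The SAP applies this generally: "The p-value will be calculated as above even if" the actual second stage has its planned size. It then states: "The point estimate of response rate and the corresponding 90% confidence interval will be obtained by inverting the hypothesis testing". The estimate is the tested rate at which p = 0.5, and the 90% interval is the set of rates with p between 0.05 and 0.95.

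SAP 3.3.1.2 says of the one additional patient per cohort: "In all cases this extra patient will be included in the main/end analysis". Neither document gives a special rule for a second stage without responses.

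**The concern.** An estimate of the response rate should not fall as responders are added at a fixed sample size, and it should use the responses from both stages. The SAP formula appears to fail on both counts when x2 = 0. SAP 5.6 describes the ORR analysis as the study's only formal statistical analysis, and its purpose is to judge whether activity warrants further development. For a cohort that ends just short of the rejection boundary, that judgement rests largely on the estimate and interval. An interval that does not depend on how many patients responded would mislead the people making it.

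**Working it through.** **Inputs (SAP Table 4 and 3.3.1.2).** Design values as π0 / π1 / n1 / n / r1 / r2:
- colorectal 5% / 20% / 13 / 27 / 0 / 3
- ovarian 7% / 25% / 16 / 26 / 1 / 4
- cervical 10% / 30% / 15 / 25 / 1 / 5

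With the extra patient the totals are 28, 27 and 26. I place that patient in stage 2, so n2* = 15, 11 and 11, and keep stage 1 at the Table 4 size. Splits are written x1+x2.

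**Assumption.** A(x, n2, π*) = P(X2 > r2 − x | n2, π*), the same form as the left side of step i.

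**Reproducing the plan.** SAP 3.3.1.2 says the design "yields a type I error rate of 0.05 and statistical power of 0.80 for each of the three main cohorts". Summing P(X1 = x)·P(X2 > r2 − x) over x > r1 gives attained type I error and power of 0.0416 and 0.801 (colorectal), 0.0306 and 0.803 (ovarian), and 0.0328 and 0.802 (cervical). Power reproduces, and 0.05 is the ceiling of a discrete design. At the planned cervical size of 25, splits 3+3, 4+2 and 5+1 all give p = 0.0328, as the SAP's stated simplification requires. This supports the reading of A.

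**What happens at x2 = 0.**
1. The right side of step i is P(X2 ≥ 0) = 1 for every tested rate and every n2*.
2. For x1 ≤ r2 the left side equals 1 only at π* = 1.
3. At π* = 1 every A(x, n2, 1) is 1.
4. Step ii becomes p(π) = P(X1 > r1 | n1, π). Neither x1 nor n2* remains.

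Written out:
- colorectal: p = 1 − (1−π)^13
- ovarian: p = 1 − (1−π)^16 − 16π(1−π)^15
- cervical: p = 1 − (1−π)^15 − 15π(1−π)^14

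For cervical at π = 0.10, p = 1 − 0.2059 − 0.3432 = 0.451. Setting p to 0.5, 0.05 and 0.95 gives the estimate and limits in the third column below. They apply to every x1 from r1+1 to r2. The last column uses total-response ordering, p(π) = P(X1 > r1 and X1+X2 ≥ observed total), inverted by the same 0.5 / 0.05 / 0.95 rule.

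| Outcome | Crude | SAP estimate (90% CI) | SAP estimate, fewer responders | Total-response ordering |
|---|---|---|---|---|
| Colorectal 3+0 of 28 | 10.7% | 5.2% (0.4–20.6%) | 1+1: 7.6% | 10.1% (3.2–23.2%) |
| Ovarian 4+0 of 27 | 14.8% | 10.3% (2.3–26.4%) | 2+1: 12.0% | 14.3% (5.5–28.6%) |
| Cervical 5+0 of 26 | 19.2% | 10.9% (2.4–27.9%) | 2+1: 12.6% | 18.1% (8.1–32.9%) |

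The other SAP results for five cervical responders of 26 are 17.3% (4+1), 18.2% (3+2) and 18.5% (2+3). One further stage-2 response moves 5+0 (10.9%, p = 0.451) to 5+1 (21.8%, p = 0.038).

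**At the planned size.** Cervical 5+0 of 25 again gives 10.9% and p = 0.451, while 4+1 gives 17.9% and p = 0.121. The SAP's simplification therefore holds for the rejection rule but not for the reported p-value, estimate or interval.

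**How often.** P(x2 = 0 and r1+2 ≤ x1 ≤ r2), with the extra patient in stage 2:

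| True ORR | Colorectal | Ovarian | Cervical |
|---|---|---|---|
| Null | 6.1% | 4.2% | 5.7% |
| 15% | 4.2% | 6.0% | 6.3% |
| Target | 1.8% | 1.8% | 1.2% |

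The exact cervical 5+0 outcome has probability 0.3% at 10%, 0.9% at 20% and 0.4% at 30%.

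**The case against.** **A is undefined.** The SAP refers to a methods paper that is not available here, and the calculation depends on how A is read. That must be declared, but it does not rescue the formula. The reading used reproduces Table 4, and any upper-tail stage-2 probability with a threshold within reach equals 1 at π* = 1, so the collapse remains.

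**No decision changes.** This stands. With x2 = 0 and x1 ≤ r2 the total is at most r2, so Table 4 does not reject. A reader might infer that type I error, power or the cohort's formal conclusion is compromised. The documents do not support that.

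**The crude rate is still shown.** This also stands. SAP 5.6.1 opens by summarising the primary endpoint under Section 5.3, which gives number and percentage, and the protocol synopsis adds a descriptive summary. A reader might infer that the observed ORR is hidden or generally halved. It is not: the model-based estimate is 49% of crude for colorectal 3+0, but 57% for cervical 5+0 and 70% for ovarian 4+0. These are the extreme splits, and each collapsed interval still contains the crude rate.

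**The reversal depends on the split.** Cervical 5+0 falls below three responders only when the three are split 2+1. A 3+0 split gives the same 10.9%.

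**Conclusion.** The defect is real and limited. When stage 2 has no responses and r1 < x1 ≤ r2, the SAP's p-value, estimate and 90% interval do not depend on the number of responders, and they can rank a cohort below one with fewer. The error lies in the inferential summary of a cohort that has already missed its boundary. At its largest, the cervical estimate is 10.9% where ordering by total responses gives 18.1%, with upper limits of 27.9% and 32.9%.

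The algebra is exact given the stated reading of A. The figures for the other splits, for the replacement and for frequency also assume Table 4 stage-1 sizes and the extra patient in stage 2. The collapsed results do not depend on n2*. The change should be made before the analysis, but the rejection rule does not need rescuing.

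**What to change.** In SAP 5.6.1, replace steps i and ii with p(π) = P(X1 > r1 and X1+X2 ≥ s), where s is the observed total. This is the sum over x from r1+1 to n1 of P(X1 = x | n1, π)·P(X2 ≥ s − x | n2*, π), using the patients actually in each stage. Keep the existing inversion for the estimate and interval. A is then no longer needed.

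The result rises with the count and does not depend on the split. For cervical totals of 2 to 6 of 26 it gives 10.9%, 12.3%, 14.9%, 18.1% and 21.7%. At planned n it equals the Table 4 rule (p = 0.0416, 0.0306 and 0.0328 at r2+1 responses for colorectal, ovarian and cervical). With the extra patient in stage 2, r2+1 responses give p = 0.046, 0.035 and 0.039, all still below 0.05.

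The cost is more than the two formula lines. The sentence citing the method and the statement in SAP 5.9 must be revised to match, and the analysis program adjusted. No data collection, sample size or design element changes.

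### The 90% interval for the primary response rate takes its upper limit from the wrong tail, so near the success threshold that limit is about 3 to 4 points too low

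*SAP*

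**What the plan says.** SAP section 5.3 sets the frame: "All tests will be one-sided and performed at the 5% significance level", and "p-values will be reported together with 2-sided 90% confidence intervals". A two-sided 90% interval implies at most 5% error in each tail.

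SAP section 5.6.1 defines the p-value through two steps. Step i matches a conditional tail of the planned design to P(X2 ≥ x2 | n2*), so the observed stage 2 count is inside the tail. With the planned stage 2 size this reduces to Simon's "2-stage design with rejection regions as in Table 4", that is, rejection when r2 + 1 "or more responses are observed in" n patients.

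The interval and the estimate "will be obtained by inverting the hypothesis testing", using that same p-value. The interval holds the null rates "such that the corresponding p-value is within [0.05, 0.95", and the rate "which gives a p-value of 0.5 will be the point estimate of the response rate". No separate lower-tail probability is defined for the upper limit.

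**The concern.** For a continuous statistic, P(observed or better) = 0.95 and P(observed or worse) = 0.05 are the same condition. For response counts they are not, because the observed count has positive probability and belongs to both tails. Taking both limits from one inclusive upper tail treats the lower limit correctly and shifts the upper limit down by one result.

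This is the only interval planned for the only formal efficacy analysis. A reader will use its upper end to judge which response rates remain plausible, and would take it to carry the 5% tail error that the 90% label promises.

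**Working it through.** **Inputs.** SAP Table 4 gives n1 = 13/16/15, n = 27/26/25, r1 = 0/1/1 and r2 = 3/4/5 for colorectal, ovarian and cervical cancer. The null rates are "5%, 7% and 10% for colorectal cancer, ovarian cancer and cervical cancer, respectively" (Protocol synopsis, Statistical Considerations). The target rates are 20%, 25% and 30% (SAP 3.3.1.2). The extra patient makes the main-analysis N 28/27/26 (SAP 3.3.1.2).

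**Formula.** Ordering results by total responders, the probability of passing stage 1 and reaching at least t responders is

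F(p; t) = Σ over x1 = r1+1 … n1 of P(X1 = x1 | n1, p) · P(X2 ≥ t − x1 | n2, p).

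**Reproducing the plan's own figures.** F(p0; r2+1) and F(p1; r2+1) at the planned n give type I error and power of 0.0416 and 0.801 (colorectal), 0.0306 and 0.803 (ovarian), and 0.0328 and 0.802 (cervical). These agree with the stated 0.05 (as a maximum) and 0.80.

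**The two upper limits.** For t observed responders:

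- As the SAP is written, F(p; t) = 0.95, so P(stopped at stage 1 or total ≤ t − 1) = 0.05.
- The matching limit solves P(stopped at stage 1 or total ≤ t) = 0.05, so F(p; t + 1) = 0.95.

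The SAP limit at t is therefore identical to the matching limit at t − 1. Example: the SAP limit at 4/28 is 26.4%, which is the matching limit for 3/28. A one-stage check shows the same thing: P(X ≥ 4 | 28) = 0.95 at 25.4%, the Clopper-Pearson upper limit for 3/28, whereas for 4/28 that limit is 29.8%.

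**Size at the smallest significant counts, extra patient included:**

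| Cohort | Result | Lower limit | Upper, as written | Upper, matching | Gap |
|---|---|---|---|---|---|
| Colorectal | 4/28 | 5.1% | 26.4% | 30.2% | 3.8 |
| Ovarian | 5/27 | 7.7% | 31.6% | 35.3% | 3.7 |
| Cervical | 6/26 | 10.6% | 36.6% | 40.6% | 4.0 |

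At the Table 4 sizes (4/27, 5/26, 6/25) the gaps are 4.0, 4.0 and 4.2 points. With the SAP's own step i/ii formula, where the matching limit is the p-value at x2 + 1 set to 0.95, the gap at these counts depends on how responders split between the stages: 3.3 to 4.7 (colorectal), 3.2 to 4.5 (ovarian), and 3.5 to 4.2 (cervical, 2 to 4 stage 1 responders). At the lowest count that passes stage 1 it is 0.6 (1/28), 0.4 (2/27) and 0.4 (2/26).

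**Error rates.** These are conditional on reaching stage 2, because no p-value, and so no interval, is defined for a cohort stopped at stage 1. They use the Table 4 sizes, total ordering, and true rates from 10% to 50%. The chance that the true rate exceeds the printed limit peaks at 10.8%, 10.7% and 10.7% in the three cohorts. The lowest coverage of the printed interval is 84.6% to 85.8%; with the matching limit it is 90.3% to 90.9%.

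**Can the printed limit exclude the target?** The p-value never exceeds P(X1 > r1), so the smallest possible upper limit solves P(X1 > r1) = 0.95. For colorectal, 1 − (1 − p)^13 = 0.95 gives p = 1 − 0.05^(1/13) = 20.6%, above the 20% target. For ovarian it is 26.4%, above 25%. For cervical it is 27.9%, below 30%, so exclusion is possible there. Example: 4/26 as 3 + 1, by the SAP formula, prints 5.3% to 29.6%; the matching interval by the same formula is 5.3% to 32.9%.

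**The case against.** The strongest reply is that nothing is decided on this limit. Futility and success rest on response counts, the p-value and the lower limit are right, and the raw count and percentage will also be reported. Average coverage among stage 2 cohorts is 91.7% to 92.7%, above the nominal 90%, because the counts are discrete. All of this stands, and it limits the consequence. It does not make the printed upper limit correct: the 5% guarantee for that tail fails at some true rates, and the limit shown belongs to a different result.

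Three stronger readings are tempting, and the documents do not support them.

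- **A weak cohort will generally appear to rule out its target rate.** This cannot happen in colorectal or ovarian cancer. In cervical cancer it depends on the split: 4/26 as 2 + 2 prints 30.2%, and 3 + 1 at N = 25 prints 30.1%, so neither excludes 30%. The cases that do are below the 6 responders needed for success. With a true cervical rate of 30%, the printed limit falls below 30% about 3% of the time (N = 25) or 4% (N = 26), within the 5% allowance.
- **Upper-tail error is inflated everywhere.** The values near 10% occur at true rates above the targets. For colorectal at N = 27 it is 5.4% at a true rate of 30% and 9.4% at 40%.
- **The point estimate is also wrong.** The rate at p = 0.5 is below the raw rate at 4/28 (13.3% against 14.3%) but above it at 1/28 (5.2% against 3.6%). It is not uniformly low, and replacing it would be a choice of estimator rather than the correction of an error.

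**Conclusion.** The point holds for the upper limit only. As written, the upper end of the 90% interval is that of the next worse result. Near and above the success threshold it is about 3 to 4 points too low; at the lowest counts that pass stage 1 the gap is under 1 point. Upper-tail error among stage 2 cohorts reaches about 10% at some true rates, where the label implies at most 5%.

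The headline figures assume total-response ordering and the full N of 28/27/26. The SAP's own formula gives gaps of similar size that vary with the stage split. The conclusion also assumes that the p-value inverted for the interval is the one defined just before it, which is how the text reads. This is a cheap reporting correction to settle before the analysis is programmed. It casts no doubt on the design, the test or the go/no-go rule.

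**What to change.** In SAP section 5.6.1, keep p = 0.05 for the lower limit and add one sentence for the upper: it is the rate at which the probability of the observed result or a worse one equals 0.05, obtained by computing the p-value with x2 + 1 in place of x2 and setting it to 0.95. Leave the point estimate as it is.

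The cost is that sentence, a few lines of code, and an interval about 3 to 4 points wider at the top for results near the threshold. No patients are added, and the test does not change.
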